**Table 3-5 Off-Treatment Phase Analysis Visit Windows for Subjects Meeting Treatment Stopping Criteria for ECG**

Nominal Visit	Off-Treatment Phase Nominal Study Day	Visit Window Study Day	
		Lower Limit	Upper Limit
Off-Treatment Day 1	1	(none)	1
Off-Treatment Week 12	84	2	210
Off-Treatment Week 48	336	211	≥ 366

The analysis windows for the Off-Treatment Phase assessments for subjects not meeting Treatment Stopping Criteria of HBV TNA, HBV RNA, HBsAg, Vital signs, Chemistry, Hematology, Coagulation, and Urinalysis are provided in Table 3-6.

The analysis windows for the NrtI-Restart Phase assessments of the same categories as the previous paragraph also follow Table 3-6.

**Table 3-6 Off-Treatment Phase for Subjects Not Meeting Treatment Stopping Criteria and NrtI-Restart Phase Analysis Visit Windows for HBV TNA, HBV RNA, HBsAg, Vital Signs, Chemistry, Hematology, Coagulation, and Urinalysis**

Nominal Visit	Off-Treatment/NrtI-Restart Phase Nominal Study Day	Visit Window Study Day	
		Lower Limit	Upper Limit
Off-Treatment/NrtI-Restart Day 1	1	(none)	1
Off-Treatment/NrtI-Restart Week 4	28	2	42
Off-Treatment/NrtI-Restart Week 8	56	43	70
Off-Treatment/NrtI-Restart Week 12	84	71	98
Off-Treatment/NrtI-Restart Week 16	112	99	126
Off-Treatment/NrtI-Restart Week 20	140	127	154
Off-Treatment/NrtI-Restart Week 24	168	155	182
Off-Treatment/NrtI-Restart Week 28	196	183	210

Nominal Visit	Off-Treatment/NrtI-Restart Phase Nominal Study Day	Visit Window Study Day	
		Lower Limit	Upper Limit
Off-Treatment/NrtI-Restart Week 32	224	211	238
Off-Treatment/NrtI-Restart Week 36	252	239	266
Off-Treatment/NrtI-Restart Week 40	280	267	294
Off-Treatment/NrtI-Restart Week 44	308	295	322
Off-Treatment/NrtI-Restart Week 48	336	323	≥ 336

The analysis windows for the Off-Treatment Phase assessments for subjects not meeting Treatment Stopping Criteria of HBV DNA, HBcrAg, and HBeAg are provided in Table 3-7.

The analysis windows for the NrtI-Restart Phase assessments of the same categories as the previous paragraph also follow Table 3-7.

**Table 3-7 Off-Treatment Phase for Subjects Not Meeting Treatment Stopping Criteria and NrtI-Restart Phase Analysis Visit Windows for HBV DNA, HBcrAg, and HBeAg**

Nominal Visit	Off-Treatment/NrtI-Restart Phase Nominal Study Day	Visit Window Study Day	
		Lower Limit	Upper Limit
Off-Treatment/NrtI-Restart Day 1	1	(none)	1
Off-Treatment/NrtI-Restart Week 12	84	2	126
Off-Treatment/NrtI-Restart Week 24	168	127	210
Off-Treatment/NrtI-Restart Week 36	252	211	294
Off-Treatment/NrtI-Restart Week 48	336	295	≥ 336

The analysis windows for the Off-Treatment Phase assessments for subjects not meeting Treatment Stopping Criteria of ECG are provided in Table 3-8.

The analysis windows for the NrtI-Restart Phase assessments of the same categories as the previous paragraph also follow Table 3-8.

**Table 3-8 Off-Treatment Phase for Subjects Not Meeting Treatment Stopping Criteria and NrtI-Restart Phase Analysis Visit Windows for ECG**

Nominal Visit	Off-Treatment/NrtI-Restart Phase Nominal Study Day	Visit Window Study Day	
		Lower Limit	Upper Limit
Off-Treatment/NrtI-Restart Day 1	1	(none)	1
Off-Treatment/NrtI-Restart Week 12	84	2	210
Off-Treatment/NrtI-Restart Week 48	336	211	≥ 366

**3.6.6. Selection of Data in the Event of Multiple Records in an Analysis Visit Window**

Depending on the statistical analysis method, single values may be required for each analysis window. If a single value is needed, but multiple valid, nonmissing measurements exist in an analysis window, records will be chosen based on the following rules:

- For baseline, the last nonmissing value on or prior to the first dose date of study drug will be selected, unless specified differently. If there are multiple records with the same time or no time recorded on the same day, the record with the lowest accession number will be used.
- For postbaseline values:
  - The record closest to the nominal day for that visit will be selected.
  - If there are 2 records that are equidistant from the nominal day, the later record will be selected.
  - If there is more than 1 record on the selected day with the same time, the retest record will be selected. If there is no clear indication for which record is the retest record, then the record with the lowest accession number will be used.

## **4. SUBJECT DISPOSITION**

### **4.1. Subject Enrollment and Disposition**

A summary of subject enrollment will be provided by treatment group for each country, Investigator within a country, and overall. The summary will present the number and percentage of subjects randomized. For each column, the denominator for the percentage calculation will be the total number of subjects analyzed for that column.

A similar enrollment table will be provided by randomization stratum. The denominator for the percentage of subjects in the stratum will be the total number of randomized subjects. If there are discrepancies in the value used for stratification assignment between the IRT and the clinical database, the value collected in the clinical database will be used for the summary. A listing of subjects with discrepancies in the value used for stratification assignment between the IRT and the clinical database at the time of data finalization will be provided. The randomization schedule used for the study will be provided as an appendix to the CSR.

A summary of subject disposition will be provided by treatment group. This summary will present the number of subjects in each of the categories listed below:

- All Randomized Analysis Set
- Full Analysis Set
- Safety Analysis Set

The number and percentage of the subjects in the following categories will be summarized using the Safety Analysis Set:

- Completed study drug VBR
- Did not complete study drug VBR with reasons for premature study drug discontinuation
- Completed study drug AB-729
- Did not complete study drug AB-729 with reasons for premature study drug discontinuation
- Completed study
- Did not complete the study with reasons for study discontinuation

For the status of study drug and study completion and reasons for premature discontinuation, the number and percentage of subjects in each category will be provided. The denominator for the percentage calculation will be the total number of subjects in the Safety Analysis Set corresponding to that column.

The following by-subject listings will be provided by subject ID number in ascending order:

- Reasons for premature study drug or study discontinuation
- Dispensed bottle number and lot number for VBR, lot number for AB-729

The proportion of subjects meeting treatment stopping criteria will be summarized. A by-subject listing detailing each subject's treatment stopping decision and the HBV DNA, HBsAg, and ALT results from their last on-treatment (i.e. week 48) study visit will be included.

## **4.2. Extent of Study Drug Exposure and Compliance**

Extent of exposure to study drug will be examined by assessing the total duration of exposure to study drug and the level of compliance relative to the study drug regimen specified in the protocol.

### **4.2.1. Duration of Exposure to Study Drug**

Total duration of exposure to each study drug will be defined as the last dose date minus the first dose date plus 1 for VBR and plus 56 days for AB-729, regardless of any temporary interruptions in study drug administration, and will be expressed in weeks using up to 1 decimal place (eg, 4.5 weeks). Duration (weeks) = Duration (days) /7. The last dose date of individual study drug is defined in [Section 3.6.3](#). If the last study drug dose date is missing, the latest date among the study drug end date, clinical visit date, laboratory sample collection date, and vital signs assessment date that occurred during the on-treatment period will be used for subjects included in the final analyses or the last available date in the database snapshot for subjects who were still on treatment at the time of an interim analysis.

The total duration of exposure to study drug will be summarized using descriptive statistics. Summaries will be provided by treatment group and study drug for the Safety Analysis Set. The expected total duration of on-treatment therapy for all subjects is 48 weeks. The distribution of subjects by the total number of weeks on therapy (ie.  $\leq 4$  weeks,  $>4-8$  weeks,  $>8-12$  weeks,  $>12-16$  weeks,  $>16-20$  weeks,  $>20-24$  weeks,  $>24-36$  weeks, and  $>36-48$  weeks,  $\geq 48$  weeks) will be presented. The cumulative distribution of subjects will also be presented using the following cutoffs: at least 1 dose,  $\geq 2$  weeks,  $\geq 4$  weeks,  $\geq 8$  weeks,  $\geq 12$  weeks,  $\geq 24$  weeks,  $\geq 36$  weeks, and  $\geq 48$  weeks. For AB-729, the distribution of subjects by number of injections will be summarized.

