### **3.5. Missing Data and Outliers**

#### **3.5.1. Missing Data**

In general, missing data will not be imputed unless methods for handling missing data are specified. Exceptions are presented in this document.

For missing last dose date of study drug, imputation rules are described in [Section 4.2.1](#). The handling of missing or incomplete dates for adverse event (AE) onset is described in [Section 7.1.5.2](#), and for prior and concomitant medications in [Section 7.3.2](#).

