#### **3.6.3. Definition of Study Phase and End of Study**

The analyses will include all the data collected in this study based on three phases defined as follows.

- **On-Treatment Phase:** when a subject is undergoing treatment with AB-729, VBR, or both per treatment group (ie, from first dose of either study drug through the last dose of VBR +1 day or last dose of AB-729 +56 days, whichever is later)
- **Off-Treatment Phase:** after a subject has discontinued AB-729, VBR, or both per treatment group, and prior to NrtI restart if applicable (ie, after the last dose of VBR +1 day or last dose of AB-729 +56 days, whichever is later, until the end of study or before the first dose of NrtI if it was restarted)
- **NrtI-Restart Phase:** after a subject has restarted NrtI, following the Off-Treatment Phase (ie, from the first dose of restarted NrtI through the end of study)

End of study is defined as when the last subject completes the last follow-up or is considered “lost to follow-up”, whichever is later.

Subjects may prematurely discontinue study drug earlier prior to the Week 48 visit. The end dates of the On-Treatment Phase may vary for individual subjects based on their last dose dates as defined in [Section 3.6.3](#).

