#### **3.6.4. Definition of Study Day**

The first dose date of VBR and of AB-729 will be calculated where applicable. Study Day 1 is defined as the first dose date of study drug, which is the minimum of the first dose dates of VBR and of AB-729 in a treatment group. If the first dose date is missing, the date of randomization will be used.

The last dose date of VBR and of AB-729 will be calculated where applicable. The last dose date of each drug will be the end date on the respective study drug end of treatment eCRF. The last dose date of study drug will be defined as the maximum of the last dose dates of VBR and of AB-729 in a treatment group.

For the On-Treatment Phase, study day will be calculated from Study Day 1 and derived as follows:

- For days prior to the first dose: Assessment Date – Study Day 1
- For postdose study days: Assessment Date – Study Day 1 + 1

For the Off-Treatment Phase, the Off-Treatment Day 1 will be defined as the day after the last dose date of study drug VBR or 56 days after last dose of AB-729, whichever is later. The off-treatment study day will be calculated from the last dose date and derived as Assessment Date – Off-Treatment Day 1 + 1.

For the NrtI-Restart Phase, the NrtI-Restart Day 1 will be defined as the first dose date of restarted NrtI. The NrtI-Restart study day will be calculated from the first dose of NrtI and derived as Assessment Date – First Dose Date of NrtI + 1.

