### **4.2.2. Study Drug Compliance**

Compliance will be calculated for study drugs VBR and AB-729.

The total number of tablets (VBR) and injections (AB-729) administered will be summarized using descriptive statistics.

The presumed total number of tablets (VBR) administered to a subject will be determined by the data collected on the drug accountability CRF using the following formula:

Total Number of Tablets Administered

$$= \left( \sum \text{No. of Tablets Dispensed} \right) - \left( \sum \text{No. of Tablets Returned} \right)$$

The presumed total volume of injections (AB-729) administered to a subject will be determined by summing the volume administered during each visit containing an injection, as reported on each relevant week's study drug administration CRF.

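### SAP 4.2.1 fills a missing last AB-729 dose date with the latest on-treatment visit or laboratory date and then adds 56 days, so the 8-week dosing interval can be counted twice

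*Combined protocol and SAP*

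**What the plan says.** SAP 4.2.1 defines exposure to each drug as last dose date minus first dose date, "plus 1 for VBR and plus 56 days for AB-729". If the last dose date is missing, it is replaced by "the latest date among the study drug end date, clinical visit date, laboratory sample collection date, and vital signs assessment date". The sentence goes on to limit the candidates: "vital signs assessment date that occurred during the on-treatment period will be used for subjects included in the final analyses". No separate rule is given for AB-729.

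The date that may be missing comes from a form. In SAP 3.6.4, "The last dose date of each drug will be the end date on the respective study drug end of treatment eCRF". That section has a fallback for a missing first dose date but none for a missing last dose date. SAP 3.5.1 supplies the pointer: "For missing last dose date of study drug, imputation rules are described in" Section 4.2.1.

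The last dose date also sets the study phases. SAP 3.6.3 runs the On-Treatment Phase "through the last dose of VBR +1 day or last dose of AB-729 +56 days, whichever is later". SAP 3.6.4 puts Off-Treatment Day 1 at the day after the last VBR dose "or 56 days after last dose of AB-729, whichever is later".

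Injections are recorded separately. SAP 4.2.2 obtains the AB-729 volume "by summing the volume administered during each visit containing an injection", from the administration CRF. Protocol 8.3.3 and Table 9 place the last AB-729 injection at Week 40, with none at Weeks 44 or 48.

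**The concern.** For a daily tablet, the latest on-treatment contact is a fair stand-in for the last dose. For an injection given every 8 weeks it is not, because the latest contact can fall up to a full interval after the injection. The 56 days in the formula already represent that interval. Adding them to a visit date that lies at its end counts the interval twice.

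At stake are the AB-729 exposure summaries and, if the imputed date carries into the phase definitions, the split of adverse events and laboratory values between On-Treatment and Off-Treatment tables (SAP 7.1.6 and 7.2.1.2). Group 2 receives no AB-729, so any distortion falls on Groups 1 and 3 only. Safety is the primary objective.

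**Working it through.** **Inputs.** Days are counted from the first dose (day 0). L is the true last AB-729 injection, V the last VBR dose, D the imputed date.

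- Exposure to AB-729 = (L − 0 + 56)/7 weeks (SAP 4.2.1).
- Off-Treatment Day 1 = max(V + 1, L + 56); in Group 3 only the second term applies (SAP 3.6.4).
- Last planned injection at Week 40, day 280 (protocol 8.3.3); Week 48 is day 336.
- Under the fallback, D replaces L in both formulas.

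**The plan's own figure.** SAP 4.2.1 expects 48 weeks on treatment. AB-729: (280 + 56)/7 = 48.0 weeks. VBR with a last dose on day 335: (335 + 1)/7 = 48.0 weeks. Both agree, so the 56 days are right when L is a real injection date.

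**Exposure with D in place of L.** The error is (D − L)/7.

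| Case | True weeks | Imputed weeks | Error |
|---|---|---|---|
| Six doses, D = Week 48 visit | (280 + 56)/7 = 48.0 | (336 + 56)/7 = 56.0 | +8.0 |
| Last injection Week 16, D = Week 24 visit | (112 + 56)/7 = 24.0 | (168 + 56)/7 = 32.0 | +8.0 |
| Group 1, AB-729 assumed stopped after Week 8, VBR to Week 48, D = Week 48 visit | (56 + 56)/7 = 16.0 | (336 + 56)/7 = 56.0 | +40.0 |

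The second case moves from the >20–24 to the >24–36 week category. The third moves from >12–16 to ≥48 weeks. It is possible because VBR keeps the subject on treatment, so later visits remain eligible as D.

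**Off-Treatment Day 1, if the imputed date is carried through SAP 3.5.1 (six doses, D = 336).**

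- Group 3: 336 becomes 392, a delay of 56 days.
- Group 1, VBR to day 336: max(337, 336) = 337 becomes max(337, 392) = 392, a delay of 55 days.
- Group 1, VBR assumed to Week 50 (day 350) while results are awaited: 351 becomes 392, a delay of 41 days.

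**Upper bound on the delay.** Let E = max(V + 1, L + 56) be the true boundary. If D ≤ E, the imputed boundary max(V + 1, D + 56) is at most E + 56. The delay therefore cannot exceed 56 days while the on-treatment limit is applied to the true period.

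**Can the limit be applied?** Section 4.2.1 does not define its on-treatment period. If it means the On-Treatment Phase of 3.6.3, that phase is itself set by the last AB-729 dose date, which is the missing value, so the limit is circular.

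**Effect on a group mean.** At the planned group sizes, one completer with an 8-week error adds 8/15 = 0.53 weeks to the Group 3 mean, or 8/30 = 0.27 weeks to the Group 1 mean.

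**The case against.** The best case for leaving the text alone is that the rule may never be used. It needs a missing end-of-treatment form date for a drug injected in clinic, with administration dates kept as accountability records (protocol 6.1.3) and a final analysis run after data cleaning. The number of injections is summarised and study drug administration is listed by subject, so an inflated duration would be visible. For a completer, 48.0 and 56.0 weeks both meet the ≥48 week cutoff. TEAEs run to end of study and all AEs are listed, so no event is lost; at most it changes table. All of this stands, and it keeps the point minor. It does not make the rule right when it is used.

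Four stronger readings are tempting, and the documents do not support them.

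- **That Off-Treatment Day 1 could slip by more than 8 weeks.** The on-treatment restriction caps the delay at 56 days if it is applied to the true period. Longer delays need the restriction to be ignored: for example 395 − 333 = 62 days with the Week 40 dose 3 days early and the Week 48 visit 3 days late. The circularity leaves that open, but the SAP does not direct it.
- **That the phase effect is stated in the SAP.** Section 4.2.1 is written for exposure. The link to the phases is an inference through the general pointer in 3.5.1.
- **That events just after NrtI withdrawal are broadly misplaced.** After the February 2023 termination, the Treatment Stopping Criteria no longer applied to subjects who then reached Week 48 (SAP 1.2). The scenario needs someone who stopped under the criteria earlier and also has a missing form date.
- **That taking the date from the end-of-treatment form is itself an error.** Nothing shows that the form would disagree with the administration CRF.

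**Conclusion.** The point holds as a defect in the fallback rule. When an AB-729 end-of-treatment date is missing, SAP 4.2.1 can overstate exposure by 8.0 weeks for a subject on schedule, and by more in Group 1 if AB-729 stops well before VBR (40.0 weeks in the assumed example). The delay to Off-Treatment Day 1 is up to 56 days in Groups 1 and 3. It rests on two assumptions: that 3.5.1 carries the imputed date into 3.6.3 and 3.6.4, and that the on-treatment limit refers to the true period.

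The number of subjects affected is unknown and probably small. The change is worth making because it is cheap, but the point does not threaten the main conclusions.

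**What to change.** In SAP 4.2.1, state that a missing AB-729 last dose date is replaced by the date of the last injection recorded on the study drug administration CRF, and that the latest-visit fallback applies to VBR only. Refer to this rule from 3.6.4, so that exposure and phase boundaries use the same date. The end-of-treatment form can remain the source for non-missing dates.

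While editing, correct the cross-reference in 4.2.1: it cites 3.6.3 for the last dose date, but the definition is in 3.6.4.

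The cost is one sentence and two cross-references. No new data are needed.

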### **4.2.2. Study Drug Compliance**

Compliance will be calculated for study drugs VBR and AB-729.

The total number of tablets (VBR) and injections (AB-729) administered will be summarized using descriptive statistics.

The presumed total number of tablets (VBR) administered to a subject will be determined by the data collected on the drug accountability CRF using the following formula:

Total Number of Tablets Administered

$$= \left( \sum \text{No. of Tablets Dispensed} \right) - \left( \sum \text{No. of Tablets Returned} \right)$$

The presumed total volume of injections (AB-729) administered to a subject will be determined by summing the volume administered during each visit containing an injection, as reported on each relevant week's study drug administration CRF.

#### 4.2.2.1. On-Treatment Compliance

The level of on-treatment compliance to the study drug will be determined by the total amount of study drug administered relative to the total amount of study drug expected to be administered during a subject's actual on-treatment period.

The level of on-treatment compliance for each study drug will be expressed as a percentage using the following formula:

On-Treatment Compliance

$$(\%) = \left( \frac{\text{Total Amount of Study Drug Administered}}{\text{Total Amount of Study Drug Expected to be Administered on Treatment}} \right) \times 100$$

Per protocol, each subject receiving VBR is expected to take three 100 mg tablets of VBR daily during the on-treatment phase. In a 48-week period, a total of 1008 tablets would be expected. Each subject receiving AB-729 is expected to receive a 60 mg (0.33 mL) injection once every 8 weeks during the on-treatment phase. In a 48-week period, a total of 360 mg (2 mL) over 6 injections would be expected.

For subjects who prematurely discontinue, the denominator will be the total amount of study drug expected to be administered by the date of premature discontinuation.

Descriptive statistics for the level of on-treatment compliance with the number and percentage of subjects belonging to compliance categories (e.g.,  $\leq 80\%$ ,  $> 80-90\%$ , and  $\geq 90\%$ ) will be provided by treatment group for the Safety Analysis Set.

A by-subject listing of study drug administration and drug accountability will be provided by subject ID number in ascending order and visit in chronological order.

### 4.3. Protocol Deviations

Subjects who did not meet the eligibility criteria for study entry but enrolled in the study will be summarized. The number and percentage of subjects who did not meet at least 1 eligibility criterion will be provided for specific criteria by treatment group based on the All Randomized Analysis Set. A by-subject listing will be provided for those subjects who did not meet at least 1 eligibility (inclusion or exclusion) criterion. The listing will present the eligibility criterion (or criteria if more than 1 deviation) that subjects did not meet and related comments, if collected.

Protocol deviations (PDs) occurring after subjects entered the study are documented during routine monitoring. The number and percentage of subjects with important PDs (IPDs) by deviation category will be summarized by treatment group for All Randomized Analysis Set. A table will be provided to summarize any COVID-19 related PDs with the deviation reason by treatment groups. A by-subject listing will be provided for those subjects with any protocol deviations.

A table will be provided to summarize any COVID-19 related PDs with the deviation reason by treatment groups. Any visits that were not performed will be summarized by reason (ie, adverse event, COVID-19 restrictions, and Other). A listing of subjects who had study disruption due to COVID-19 will be provided with a description.

